5.1.3 Concomitant medication date imputation

Incomplete day

Incomplete start day will be imputed as MAX(date of study day 1, earliest possible start date).

Incomplete end day will be imputed as MIN(EoS, latest possible end date).

Earliest possible start/end date is calculated on the eCRF page and refers to the first day of the corresponding month. *Latest possible start/end date* is calculated on the eCRF page and refers to the last day of the corresponding month.

Incomplete day/month

Incomplete start day/month will be imputed as MAX(date of study day 1, 1st January of the year entered).

Novartis	Confidential	Page 23 of 34
SAP v1.1		CAMG334ADE03

Incomplete end day/month will be imputed as MIN(EoS, 31th December of the year entered).

Incomplete day/month/year

Incomplete day/months/year will not be imputed.

5.1.4 **Prior therapies date imputation**

Incomplete day

Incomplete start day will be imputed as *earliest possible start date*.

Incomplete end day will be imputed as MIN (date of the day prior to study day 1, *latest possible end date*).

Incomplete day/month

Incomplete start day/month will be imputed as 1st January of the year entered.

Incomplete end day/month will be imputed as MIN(31th December of the year entered, date of the day prior to study day 1).

Incomplete day/month/year

Incomplete start date will be imputed as very early date

Incomplete end date will be imputed as a date of the day prior to study day 1.

5.1.5 Post therapies date imputation

Not applicable

5.1.6 Other imputations

5.1.6.2 Aura

The presence of aura in patient demographics is defined as at least one day with aura during baseline epoch in the HER-MES trial.

5.1.6.3 Disease duration

Disase duration at baseline will be calculated from *derived age* at informed consent for the HER-MES trial and *age at migraine onset* documented in headache and migraine frequency history form in HER-MES trial.

5.2 AEs coding/grading

Adverse events are coded using the Medical dictionary for regulatory activities (MedDRA) terminology. Already coded terms will not be recoded in case of MedDRA version changes.

Severity of adverse events is graded by investigator (mild, moderate, severe) and reflected in the eCRF.

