## 11.2 **Database management and quality control**

Novartis personnel (or designated CRO) will review the data entered by investigational staff for completeness and accuracy. Electronic data queries stating the nature of the problem and requesting clarification will be created for discrepancies and missing values and sent to the investigational site via the EDC system. Designated investigator site staff are required to respond promptly to queries and to make any necessary changes to the data.

Concomitant treatments and prior medications entered into the database will be coded using the WHO Drug Reference List, which employs the Anatomical Therapeutic Chemical classification system. Medical history/current medical conditions and adverse events will be coded using the Medical Dictionary for Regulatory Activities (MedDRA) terminology.

At the conclusion of a non-IRT study, the occurrence of any emergency code breaks will be determined after return of all code break reports and unused supplies to Novartis.

Novartis	Confidential	Page 48
Clinical trial protocol V01	Protocol No. CAMG334ADE03	

Once all the necessary actions have been completed and the database has been declared to be complete and accurate, it will be locked and the treatment codes will be unblinded and made available for data analysis. Any changes to the database after that time can only be made after written agreement by Novartis development management.

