2.1.1.3 Demographics and other baseline characteristics

Patient demographic and baseline characteristic data have been collected on all patients including: age, sex, race, relevant medical history/current medical condition present before signing informed consent for trial CAMG334ADE01 (HER-MES). These data from HER-MES trial will also be included in the analyses described in this SAP.

Prior headache characteristics and previous headache medication history prior to treatment in trial CAMG334ADE01 (HER-MES), including information on the suitability for migraine prophylactics will be collected as part of baseline characteristics.

Relevant medical history/current medical conditions present before signing the Informed consent for trial CAMG334ADE03 (APOLLON) will be recorded on the 'Medical History' eCRF page. Medical history and adverse events from the HER-MES trial represent medical history in APOLLON trial.

Novartis	Confidential	Page 11 of 34
SAP v1.1		CAMG334ADE03

Prior and concomitant medication in APOLLON trial will be recorded on the 'Prior/concomitant medication/non-drug therapies' eCRF page. Ongoing medication from HER-MES will be taken over on the APOLLON eCRF page 'Ongoing concomitant medication/non-drug therapies from HER-MES'. All concomitant medication from the HER-MES trial will be taken over as prior resp. concomitant medication. A comparison between the data records takes place to filter out duplicate entries.

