2.1.1.4 Safety endpoints

Safety summaries (tables, figures) include only data from the on-treatment period with the exception of baseline data which will also be summarized where appropriate (e.g. change from baseline summaries). In addition, a separate summary for death including on treatment and post treatment deaths will be provided. In particular, summary tables for adverse events (AEs) will summarize only on-treatment events, with a start date during the on-treatment period (treatment-emergent AEs).

Discontinuation of treatment due to AE during the Treatment Epoch

Discontinuation of treatment due to AE during the Treatment Epoch is determined by the flag on the Treatment Completion eCRF page. "Death" as a reason for treatment discontinuation will be also included in AEs leading to treatment discontinuation.

Treatment-Emergent Adverse Event (TEAE)

Treatment emergent adverse events are defined as AEs occurred on or after the first dose of study treatment. AEs registered prior and after the first dose of study treatment are considered as treatment emergent if they have increased severity based on preferred term any time after the first dose of study treatment.

In case of missing data on a day of AE start date, the AE is considered as treatment emergent if *date of first dose of study treatment* \leq *latest possible start date*

Please, see section 5.1.2 AE date imputation for "latest possible start date" definition.

Serious Adverse Event (SAE)

SAEs are determined by the flag on the Adverse Events eCRF page.

Treatment-Related Adverse Event

Treatment-emergent adverse event is defined as treatment-related, if investigator considered it as having a reasonable possibility to be related to study treatment, which is reflected in the eCRF with a corresponding flag.

Adverse Event leading to dose adjustment

Adverse event is defined as leading to dose adjustment if at least one of the following actions was taken with the study treatment due to AE:

- dose increased
- dose reduced
- drug interrupted
- drug withdrawn

Novartis	Confidential	Page 12 of 34
SAP v1.1		CAMG334ADE03

Duration of exposure to IMP

For all calculations of exposure, dose date refers to receiving dose > 0. The duration of exposure to IMP is computed as min (last IMP dose date + 27, EoS date) – first IMP dose date + 1 either including the time of drug holiday or excluding the time of drug holiday.

Subject Incidence

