2.8.1 Adverse events (AEs)

In the frame of safety analysis the following treatment-emergent AE types will be considered:

- Any AE
- Study treatment related AE
- AE leading to study treatment discontinuation
- AE leading to dose adjustment (including study treatment discontinuation)
- Serious AE (SAE)
- Study treatment related SAE
- SAE leading to study treatment discontinuation
- Death

The Medical Dictionary for Regulatory Activities (MedDRA) version 24.1 or later will be used to code all adverse events (AE) to a system organ class (SOC) and a preferred term (PT).

Novartis	Confidential	Page 19 of 34
SAP v1.1		CAMG334ADE03

The SOCs will be presented in the alphabetic order and PTs will be ordered within the SOCs by decreasing order of frequency.

The number (and percentage) of subjects with treatment emergent adverse events (events started after the first dose of study medication or events present prior to start of treatment but increased in severity based on preferred term) will be summarized in the following ways:

- by primary system organ class and preferred term.
- by primary system organ class, preferred term and maximum severity
- by Standardized MedDRA Query (SMQ) and preferred term

If a patient reported more than one adverse event with the same PT, the adverse event with the greatest severity will be presented. If a patient reported more than one adverse event within the same primary system organ class, the patient will be counted only once with the greatest severity at the system organ class level, where applicable.

The overview of adverse events occurring during treatment will additionally be presented by starting dose (70mg/140mg).

All AEs, deaths (see see section 2.8.2 Deaths for details), SAEs and AEs leading to permanent study drug discontinuation will be listed separately.

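### SAP 5.2 bars recoding when the MedDRA version changes and no single version is fixed, so the descriptive AE tables can mix dictionary versions

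*SAP*

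**What the plan says.** SAP 5.2 on AE coding and grading: "Already coded terms will not be recoded in case of MedDRA version changes".

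SAP 2.8.1 on the dictionary: "The Medical Dictionary for Regulatory Activities (MedDRA) version 24.1 or later will be used to code all adverse events (AE"). It describes this coding as assignment to an SOC and a PT. Protocol 11.2 says only that "adverse events will be coded using the Medical Dictionary for Regulatory Activities (MedDRA) terminology", with no version and no rule for a change of version.

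SAP 2.8.1 then tabulates patients with treatment-emergent AEs by SOC and PT, by SOC, PT and maximum severity, and "by Standardized MedDRA Query (SMQ) and preferred term". Repeat events are collapsed by identical label: "If a patient reported more than one adverse event with the same PT, the adverse event with the greatest severity will be presented". At SOC level a patient is counted once.

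Data from the preceding trial also enter. SAP 2.1.1.3: "Medical history and adverse events from the HER-MES trial represent medical history in APOLLON trial". SAP 2.3.3 summarises that history by SOC and PT. The MedDRA version in which the HER-MES terms were coded is not stated.

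**The concern.** The rule in 5.2 foresees a version change and settles it by leaving old codes as they are. The floor in 2.8.1 lets later events be coded in a newer version. Taken together, they allow a mixed-version AE dataset and rule out the usual remedy.

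The safety tables work by matching labels. A PT row gathers events that carry the same PT, the severity rule collapses episodes that carry the same PT, and an SMQ row gathers events whose PT is on a list. If a term is renamed, moved or demoted between versions, or an SMQ list is revised, the match can fail for reasons unrelated to what happened to the patient.

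This is a single-arm study of long-term safety with no hypothesis test, so readers will rely on these tables to see which events occurred and how often. SAP 2.8.1.1 declares special-interest events and AE grouping not applicable. That leaves the SMQ table as the only grouping by medical concept in the SAP text available.

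**Working it through.** The documents give no figure for this point, so there is none to reproduce. The check is mainly textual.

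**1. Do the two SAP rules permit mixed versions?** SAP 5.2 keeps each code once it is assigned. SAP 2.8.1 gives a minimum version and no maximum. The protocol adds neither a version nor a harmonisation step. An event coded before a version change and one coded after it may therefore sit in different versions, and nothing in the available text brings them together before analysis.

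**2. Which outputs depend on the PT label?**

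| Output | Depends on PT, SOC or SMQ label? |
|---|---|
| Primary AE rate (SAP 2.5.2: AEs over time under treatment) | No |
| Discontinuation due to AE or other reasons (SAP 2.6) | No; taken from the completion page |
| Any AE, SAE, death (overall counts) | No |
| SOC/PT table | Yes |
| SOC/PT by maximum severity | Yes; collapses on identical PT |
| SMQ/PT table | Yes; also depends on the version of the SMQ list, which is not named |
| Medical history by SOC/PT, with HER-MES terms | Yes |

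SAP 2.1.1.1 also defines a rate that counts patients instead of events. That rate does not depend on the label either.

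**3. How long is the window?** Treatment is 128 weeks and follow-up 4 weeks (SAP 1.1), so 128 + 4 = 132 weeks per patient. The interval at which new versions are adopted is not in the documents. Whole intervals within 132 weeks, by assumption:

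- every 26 weeks: 132/26 = 5.1, about 5 changes
- every 52 weeks: 132/52 = 2.5, about 2 changes
- every 132 weeks: 1 change
- never: 0 changes

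The range is 0 to 5, and the documents do not place the trial within it.

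**4. What would one split look like?** This shows the mechanism and is not an estimate. Take the lower expected enrolment of 563 (SAP 1.1). Assume one PT with a true subject incidence of 5%: 0.05 × 563 = 28.15, so 28 patients. Assume that this term is relabelled at a version change and that each patient has events on one side only.

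| Share coded after the change | Old row | New row |
|---|---|---|
| 0% | 28/563 = 4.97% | 0 |
| 10% | 25/563 = 4.44% | 3/563 = 0.53% |
| 25% | 21/563 = 3.73% | 7/563 = 1.24% |
| 50% | 14/563 = 2.49% | 14/563 = 2.49% |

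A patient with one episode on each side would appear in both rows. If both labels lie in the same SOC, the once-per-patient rule still gives the correct SOC total. If the term moved to another SOC, that patient is counted in both. A term that did not change between versions is not split at all.

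**The case against.** **The defence.** Neither document shows that a version change took place or that each new release would be adopted. No affected term or SMQ is identified. The rule might fix only the choice of coded term, with PT and SOC read from one version at lock. Output details are deferred to the table shells, which may name a version. All AEs, SAEs and AEs leading to discontinuation are also listed individually, so no event is lost from the report.

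**What stands.** The harm is conditional and limited to descriptive tables. The softer reading of 5.2 is possible but not the natural one, because SAP 2.8.1 treats coding as assignment to SOC and PT; if it was intended, the SAP needs to say so. Shells that we cannot see do not override an explicit rule in the SAP.

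**Stronger readings a reader might infer, which the documents do not support:**

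- *That the treatment-emergent definition fails.* One branch does rest on PT: an AE recorded before dosing counts "if they have increased severity based on preferred term any time after the first dose of study treatment". But the main branch reads "Treatment emergent adverse events are defined as AEs occurred on or after the first dose of study treatment", so a worsening recorded as a new event qualifies by its date whatever its PT. Non-serious AEs are collected only from the Baseline visit (Protocol Table 8-1, footnote 5), which leaves few pre-dose events to match. No rule says that HER-MES history is used in the severity comparison.
- *That the bias always runs towards fewer patients per term.* A patient can also be duplicated across two PTs, and terms merged in a later version could enlarge a row.
- *That 5.2 contradicts the 24.1 floor.* This would need an AE of this trial coded before 24.1, and none is shown.

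**Conclusion.** The point holds as a minor one. Followed literally across a version change, the SAP leaves AE codes in more than one MedDRA version while its tables assume one. PT and SOC rows can then be split, a patient can be counted under two PTs, and the SMQ table can miss a frozen term.

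This rests on two conditions: that the version in use changes while events are being coded, and that some of the terms or SMQ lists concerned differ between versions. The documents foresee the first without showing it and are silent on the second. The number of changes and of affected patients therefore cannot be derived, and the illustration should not be quoted as an expected size.

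The study's main conclusions are not at risk, since its primary and secondary endpoints do not use the labels. For the carried-over HER-MES terms, the weakness is mainly that their coding version is not given.

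**What to change.** Replace the sentence in SAP 5.2 with a rule that, before each database lock or data cut (interim and final), all AE terms and all history terms carried over from HER-MES are brought to one named MedDRA version. Alternatively, state that one named version is frozen for the whole trial and that the HER-MES terms are brought to it. In either case, take the SMQs from that same version, print the version in the tables, and amend SAP 2.8.1 to name it in place of the open-ended floor.

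The cost is SAP wording, one recoding run and a coder's check of the changed terms. No new data are needed. The small downside is that some interim rows may differ from the final ones if the version moves between the two; a footnote giving the version would explain this.

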5.3 Laboratory parameters derivations

Not applicable

5.4 Statistical models

5.4.1 Analysis supporting primary objective(s)

See section 2.5 Analysis supporting primary objective(s).

5.4.2 Analysis supporting secondary objective(s)

See section 2.6 Analysis supporting secondary objectives.

5.5 Rule of exclusion criteria of analysis sets

Exclusion criteria of analysis sets are complementary to those used for corresponding analysis set definitions (see section 2.2 Analysis sets).

Novartis SAP v1.1	Confidential	Page 28 of 34 CAMG334ADE03

5.8 **Abnormal laboratory value definitions**

5.8.1 Liver event and laboratory trigger definitions

The following table defines the threshold for laboratory triggers and liver events. Abnormal laboratory values are listed and the violated threshold is indicated.

								Med	ical alerts		
Parameter	Labcode	TP	Age	Gender	Unit			-	+	+ +	+ + +
Haemoglobin	HB		16	F	a/dl	8.5	9.5	12.0	16.0	18.5	23.0
			16	F	mmol/l	5.3	5.9	7.4	9.9	11.5	14.3
			16	M	g/dl	8.5	9.5	14.0	18.0	18.5	23.0
			16	M	mmol/l	5.3	5.9	8.7	11.2	11.5	14.3
Haematocrit	HK		17	F	%	25.0	30.0	35.0	45.0	54.0	60.0
			17	F	И	0.25	0.30	0.35	0.45	0.54	0.60
			17	M	%	25.0	30.0	39.0	50.0	54.0	60.0
			17	м	I/R	0.25	0.30	0.39	0.50	0.54	0.60
Red Blood Cells	ERY		17	F	Mio/cmm	2.00	3.60	4.00	5.10	5.80	7.50
			17	F	Tpt/I	2.00	3.60	4.00	5.10	5.80	7.50
			17	М	Mio/cmm	2.00	3.80	4.50	5.90	6.20	7.50
			17	М	Tpt/I	2.00	3.80	4.50	5.90	6.20	7.50
White Blood Cells	LEUK		19		/cmm	2000	3000	4000	10000	12000	20000
			19		Gpt/I	2.0	3.0	4.0	10.0	12.0	20.0
			13		/cmm	1000		4500	10500		35000
			13		Gpt/I	1.0		4.5	10.5		35.0
Basophils	BASO				%				2.0	4.0	10.0
					I/I				0.020	0.040	0.100
Basophils, abs.	BASOAB				/cmm				100	200	500
					Gpt/I				0.100	0.200	0.500
Eosinophils	EOS				%				5.0	8.0	15.0
					1/1				0.050	0.080	0.150
Eosinophils, abs.	EOSAB				/cmm				500	800	1500
					Gpt/I				0.500	0.800	1.500
Lymphocytes	LYMP		3		%	10.0	15.0	20.0	55.0	65.0	70.0
			3		1/1	0.100	0.150	0.200	0.550	0.650	0.700

Novartis SAP v1.1

								Med	ical alerts		
Parameter	Labcode	TP	Age	Gender	Unit			-	+	+ +	+ + +
lymphocytes abs					lomm	800	000	1000	2500	2800	4200
Lymphocytes, abs.	LIMITAD				Cet/	000	0.000	1 000	3500	2 000	4200
					Gpti	0.600	0.900	1.000	3.500	3.000	4.200
Monocytes	MONO				%			1.0	12.0	15.0	18.0
					1/1			0.010	0.120	0.150	0.180
Monocytes, abs.	MONOAB				/cmm			200	800	1100	1400
					Gpt/I			0.200	0.800	1.100	1.400
Neutrophils	NEUT		3		%	25.0	30.0	36.0	75.0	80.0	85.0
			3		1/1	0.25	0.30	0.36	0.75	0.80	0.85
Neutrophils, abs.	NEUTAB				/cmm	1000	1500	2000	7500	8000	9000
					Gpt/I	1.000	1.500	2.000	7.500	8.000	9.000
Platelets	THROM				T/cmm	50	120	140	440	500	600
					Gpt/I	50	120	140	440	500	600
Serum albumin, chem.	ALB		19		a/dl	2.00	3.00	3.50	5 20	5 70	6.00
,			19		a/l	20.0	30.0	35.0	52.0	57.0	60.0
			15		a/dl	2.00	2 60	3 20	4 50	5.30	6.00
			15		a/l	20.0	26.0	32.0	45.0	53.0	60.0
Alk Phosphatase	AP		10	F	13/1			35	104	300	700
Aik. Thospitatuse	~		10	F	umol/sl			0.58	1 74	5.01	11 60
			10	M	11/1			40	120	200	700
			19	M	umol/sl			0.67	2 15	5.01	11 69
			17	E	11/1			45	2.10	750	900
			17	F	umol/el			0.75	1 45	12.53	12.26
			17	M	µ110//SI			0.75	1.40	750	000
			17	IVI NA	umel/el			0.00	2.40	10.50	10.00
			17	IVI	µmol/si			0.92	2.49	12.53	13.30

							Medi	cal alerts		
Parameter	Labcode	TP	Age	Gender	Unit	 	-	+	+ +	++-
ALT (SGPT)	GPT		18	F	U/I		10	35	100	80
			18	F	µmol/sl		0.17	0.58	1.67	13.3
			18	M	U/I		10	50	100	80
			18	м	µmol/sl		0.17	0.84	1.67	13.3
AST (SGOT)	GOT		18	F	U/I		10	35	100	80
			18	F	µmol/sl		0.17	0.58	1.67	13.3
			18	М	U/I		10	50	100	80
			18	M	µmol/sl		0.17	0.84	1.67	13.3
gGT	GGT		20	F	U/I		6	42	100	60
			20	F	µmol/sl		0.10	0.70	1.67	10.0
			20	M	U/I		10	71	100	60
			20	M	µmol/sl		0.17	1.19	1.67	10.0
			14	F	U/I		6	23	100	60
			14	F	µmol/sl		0.10	0.38	1.67	10.0
			14	M	U/I		6	30	100	60
			14	М	µmol/sl	 	0.10	0.50	1.67	10.0
LDH	LDH		16	F	UA		135	214	350	60
			16	F	µmol/sl		2.25	3.57	5.85	10.0
			16	M	U/I		135	225	350	60
			16	M	umol/sl		2.25	3.76	5.85	10.0

Novartis SAP v1.1

							Medical alerts						
Parameter	Labcode	TP	Age	Gender	Unit			~	+	+ +	+++		
Calcium	CA		91	F	mmol/l	1.70	1.85	2.09	2.62	2.80	2.90		
			91	F	mg/dl	6.8	7.4	8.4	10.5	11.2	11.6		
			91	M	mmol/l	1.70	1.85	2.12	2.47	2.80	2.90		
			91	M	mg/dl	6.8	7.4	8.5	9.9	11.2	11.6		
			61	F	mmol/l	1.70	1.85	2.14	2.61	2.80	2.90		
			61	F	mg/dl	6.8	7.4	8.6	10.4	11.2	11.6		
			61	M	mmol/l	1.70	1.85	2.13	2.57	2.80	2.90		
			61	M	mg/dl	6.8	7.4	8.5	10.3	11.2	11.6		
			19	F	mmol/l	1.70	1.85	2.16	2.58	2.80	2.90		
			19	F	mg/dl	6.8	7.4	8.6	10.3	11.2	11.6		
			19	M	mmol/l	1.70	1.85	2.19	2.60	2.80	2.90		
			19	M	mg/dl	6.8	7.4	8.8	10.4	11.2	11.6		
			13	F	mmol/l	1.70	1.85	2.26	2.58	2.80	2.90		
			13	F	mg/dl	6.8	7.4	9.0	10.3	11.2	11.6		
			13	M	mmol/l	1.70	1.85	2.27	2.61	2.80	2.90		
			13	м	mg/dl	6.8	7.4	9.1	10.4	11.2	11.6		
Magnesium	MGLG		91		mmol/l	0.50	0.60	0.70	0.95	1.10	1.80		
			91		mg/dl	1.22	1.46	1.70	2.31	2.67	4.38		
			60		mmol/l	0.50	0.60	0.66	0.99	1.10	1.80		
			60		mg/dl	1.22	1.46	1.60	2.41	2.67	4.38		
			21		mmol/l	0.50	0.60	0.66	1.07	1.10	1.80		
			21		mg/dl	1.22	1.46	1.60	2.60	2.67	4.38		
			13		mmol/l	0.50	0.60	0.70	0.91	1.10	1.80		
			13		mg/dl	1.22	1.46	1.70	2.21	2.67	4.38		

						Medical alerts					
Parameter	Labcode	TP	Age	Gender	Unit			-	+	+ +	+ + +
Phosphate	PO4		19		mg/dl	1.9	2.3	2.5	4.5	6.8	8.7
			19		mmol/l	0.60	0.75	0.81	1.45	2.20	2.80
			16	F	mg/dl	1.9	2.3	2.5	4.8	6.8	8.7
			16	F	mmol/l	0.60	0.75	0.80	1.55	2.20	2.80
			16	м	mg/dl	1.9	2.3	2.6	5.0	6.8	8.7
			16	м	mmol/l	0.60	0.75	0.85	1.60	2.20	2.80

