# 10.2 Additional Safety Monitoring

## 10.2.1 Liver safety monitoring

To ensure subject safety and enhance reliability in determining the hepatotoxic potential of an investigational drug, a standardized process for identification, monitoring and evaluation of liver events has to be followed.

The following two categories of abnormalities / adverse events have to be considered during the course of the study (irrespective of whether classified/reported as AE/SAE):

- Liver laboratory triggers, which will require repeated assessments of the abnormal laboratory parameter
- Liver events, which will require close observation, follow-up monitoring and contributing factors are recorded on the appropriate CRFs

Please refer to Table 16-2 in Appendix 2 for complete definitions of liver laboratory triggers and liver events.

Every liver event defined in Table 16-2 should be followed up by the investigator or designated personnel at the trial site, as summarized below. Additional details on actions required in case of liver events are outlined in Table 16-2. Repeat liver chemistry tests (i.e. ALT, AST, TBL, PT/INR, ALP and G-GT) to confirm elevation.

- These liver chemistry repeats will be performed using the central laboratory. If results will not be available from the central laboratory, then the repeats can also be performed at a local laboratory to monitor the safety of the subject. If a liver event is subsequently reported, any local liver chemistry tests previously conducted that are associated with this event should have results recorded on the appropriate CRF.
- •
- If the initial elevation is confirmed, close observation of the subject will be initiated, including consideration of treatment interruption if deemed appropriate.
- Discontinuation of the investigational drug (refer to the Discontinuation of study treatment section), if appropriate

- Hospitalization of the subject if appropriate
- Causality assessment of the liver event
- Thorough follow-up of the liver event should include
  - These investigations can include based on investigator's discretion: serology tests, imaging and pathology assessments, hepatologist's consultancy; obtaining more detailed history of symptoms and prior or concurrent diseases, history of concomitant drug use, exclusion of underlying liver disease

All follow-up information and procedures performed must be recorded as appropriate in the eCRF.

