# 16.2 Appendix 2: Liver event and Laboratory trigger Definitions and Follow-up Requirements

Table 16-1Liver event and laboratory trigger definitions

	Definition/ threshold
LIVER LABORATORY	• $3 \times ULN < ALT / AST \le 5 \times ULN$
TRIGGERS	$\cdot$ 1.5 x ULN < TBL $\leq$ 2 x ULN
LIVER EVENTS	• ALT or AST > 5 × ULN
	
 
ALP > 2 × ULN (in the absence of known bone pathology)
 

	• TBL > 2 × ULN (in the absence of known Gilbert syndrome)
	
 
ALT or AST > 3 × ULN and INR > 1.5
 

	
 
Potential Hy's Law cases (defined as ALT or AST > 3 × ULN and TBL > 2 × ULN [mainly conjugated fraction] without notable increase in ALP to > 2 × ULN)
 

	Any clinical event of jaundice (or equivalent term)
	
 
ALT or AST > 3 × ULN accompanied by (general) malaise, fatigue, abdominal pain, nausea, or vomiting, or rash with eosinophilia
 

	
 
Any adverse event potentially indicative of a liver toxicity*
 

*These events cover the following: hepatic failure, fibrosis and cirrhosis, and other liver damage- related conditions; the non-infectious hepatitis; the benign, malignant and unspecified liver neoplasms TBL: total bilirubin; ULN: upper limit of normal	

Table 16-2	Follow up requirements for liver events and laboratory triggers
------------	---

Criteria	Actions required	Follow-up monitoring
Potential Hy's Law case a	
 
Discontinue the study treatment immediately
 
Hospitalize, if clinically appropriate
 
Establish causality
 
Record the AE and contributing factors (e.g., conmeds, med hx, lab) in the appropriate CRF
 
	ALT, AST, TBL, Alb, PT/INR, ALP and GGT until resolution ° (frequency at investigator discretion)
ALT or AST	, , , ,	
> 8 × ULN	
 
Discontinue the study treatment immediately
 
Hospitalize if clinically appropriate
 
Establish causality
 
	ALT, AST, TBL, Alb, PT/INR, ALP and GGT until resolution c (frequency at investigator discretion)
	
 
Record the AE and contributing factors (e.g., conmeds, med hx, lab) in the appropriate CRF
 
	
1.5 immediately A • Hospitalize, if clinically (f	ALT, AST, TBL, Alb, PT/INR, ALP and GGT until resolution c	
		(frequency at investigator discretion)
	Establish causality	

Novartis Clinical trial protocol V01 Confidential Protocol No. CAMG334ADE03

Criteria	Actions required	Follow-up monitoring

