2.8.3 Laboratory data

Summary statistics of laboratory hematology and blood chemistry results will be presented as absolute values as well as change from baseline by visit and laboratory test category. Change from baseline will be summarized for each time point and only for patients with both, baseline and post-baseline assessment. Shift tables will be used to compare baseline to the worst on-treatment value.

All laboratory data with clinically notable values will be listed by subject and visit. Abnormal values will be marked according to the definitions of the central laboratory (see section 5.8 Abnormal laboratory value definitions).

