2.12 Biomarkers

Not applicable

3 Sample size calculation

In general, the 750 subjects randomized for clinical trial CAMG334ADE01 will be eligible for participation in the open-label study. It is estimated that approximately 75% to 85% of the study population meaning 563~638 subjects will enroll in the open-label study thus allowing the collection of long-term safety, efficacy and quality of life data of a large group of patients.

In the three-year open-label phase II study 20120178 the proportion of patients reporting at least one AE was 87%. Based on this finding event rates and precisions were calculated for the proposed 128-week trial for the primary endpoint. In conclusion a study population of at least 500 patients was found to be sufficient for the primary endpoint with an adequate range in precision.

The calculation of effect size and precision for the secondary endpoints is based on the proportion of study discontinuation rates in the three-year open-label phase II study 2012017. 4.2% of 383 patients discontinued this trial due to adverse events. Effect size and precision for the proposed study with at least 500 patients were calculated. In conclusion a study population of at least 500 patients was found to be sufficient for the secondary endpoints with an adequate range in precision.

Novartis	Confidential	Page 22 of 34
SAP v1.1		CAMG334ADE03

4 Change to protocol specified analyses

Contrary to what was stated in the protocol, an interim analysis will be conducted. For details please refer to section 2.14 Interim analysis.

5 Appendix

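### SAP 5.8.1 presents central-laboratory alert limits as the liver trigger and liver event thresholds, but the visible ALT, AST and ALP limits are not those of Protocol Table 16-1.

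*SAP*

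**What the plan says.** SAP 5.8.1 carries almost the same title as Protocol Table 16-1. Its lead-in reads "The following table defines the threshold for laboratory triggers and liver events", followed by "Abnormal laboratory values are listed and the violated threshold is indicated". The table itself has the column header 'Medical alerts' and gives limits by sex and age in fixed units. It begins with haemoglobin and runs through blood counts, albumin, enzymes and electrolytes, so most of its rows have nothing to do with the liver.

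SAP 2.8.3 describes the same limits differently: "Abnormal values will be marked according to the definitions of the central laboratory", with a cross-reference to section 5.8.

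Protocol 10.2.1 sends the reader to Appendix 2 "for complete definitions of liver laboratory triggers and liver events". There, Table 16-1 works in ULN multiples:

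- ALT/AST laboratory trigger: above 3x and up to 5x ULN.
- ALT/AST liver event: "ALT or AST > 5 × ULN".
- ALP liver event: greater than "2 × ULN (in the absence of known bone pathology".
- Further criteria: bilirubin bands, combinations with INR or bilirubin, and clinical criteria.

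**The concern.** One table is given two jobs. As a general abnormality table it is ordinary. As the definition of liver triggers and events, which is what 5.8.1 calls it, it appears to use different cut-offs from the protocol. A programmer who follows 5.8.1 literally would print a threshold next to each liver value that is not the protocol's threshold. A reader of the listing could then not tell from the mark whether a subject met a trigger, met an event or met neither.

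This study's primary objective is long-term safety, so the liver listing should mean what its label says. It matters most for triggers. Table 16-2 requires a repeat test and close observation for a symptom-free ALT/AST rise above 3x and up to 5x ULN, but lists no AE recording for it. The laboratory listing is therefore the natural place for such cases to be seen.

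**Working it through.** **Inputs.** From the SAP 5.8.1 table, upper alert limits in U/l:

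| Test | '+' | '++' | '+++' |
|---|---|---|---|
| ALT and AST, women | 35 | 100 | about 800 |
| ALT and AST, men | 50 | 100 | about 800 |
| ALP, women | 104 | 300 | 700 |
| ALP, men | about 129 | about 300 | about 700 |

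Two readings are needed because the extracted text is damaged; neither is held against the plan.

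- The ALT/AST '+++' entry is cut off in U/l. Its µmol/sl row shows 13.3, and 13.3 × 60 = 798, read as 800.
- The men's ALP row prints 120 and 200 in U/l, but 2.15 and 5.01 in µmol/sl. Then 2.15 × 60 = 129 and 5.01 × 60 = 301, read as 300. The women's row pairs the same 5.01 with 300.

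From Protocol Table 16-1: ALT/AST trigger >3x to 5x ULN, ALT/AST event >5x ULN, ALP event >2x ULN.

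**Step 1: ALT/AST, without assuming a ULN.** If two of the SAP limits were the protocol's 3x and 5x limits, their ratio would be 5/3 = 1.67.

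- Women: 100/35 = 2.86, then 800/100 = 8.
- Men: 100/50 = 2, then 800/100 = 8.
- Skipping a column: 800/35 = 22.9 and 800/50 = 16.

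None is 1.67. Put another way, '++' = 3x needs a ULN of 100/3 = 33, while '+++' = 5x needs a ULN of 800/5 = 160. No single ULN satisfies both.

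**Step 2: what the '++' mark covers.** Assume a value is marked by the highest limit it exceeds, so that '++' covers 100 to 800 U/l. Write U for the ULN.

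- Some trigger values fall in '++' if 5U > 100, that is U > 20 (and 3U < 800, which holds for all U considered here).
- Some event values fall in '++' if 5U < 800, that is U < 160.

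So for any ULN between 20 and 160 U/l, a trigger and an event can carry the same mark. Plausible ULNs lie well inside this range. Taking '+' as the ULN gives 35 and 50. Treating the Protocol 16.1 limits (ALT 90/123, AST 93/111) as 3x ULN gives 30 to 41. Over 30 to 50 U/l the event limit is 5 × 30 = 150 to 5 × 50 = 250, always inside '++'.

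**Step 3: ALP, which does need a ULN.** Take '+' as the ULN; the columns are not labelled, so this is an assumption. Protocol 16.1 supports it for ALP, because its limits are exact multiples of these values: 832/104 = 8 and 1032/129 = 8.

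- Women: event limit 2 × 104 = 208; '++' starts at 300, and 300/104 = 2.88.
- Men: event limit 2 × 129 = 258; '++' starts at 300, and 300/129 = 2.33. With 120 as the ULN, the event limit is 240 and the ratio 2.5.

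ALP above 208 (women) or about 258 (men) and up to 300 U/l exceeds the event limit, absent known bone disease, yet is marked only '+'. The gap would close only at a ULN of 300/2 = 150 or more.

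**The case against.** The best defence is that the operative rule is stated openly. SAP 2.8.3 says the marks follow the central laboratory, and the table's header and contents show it to be a general abnormality table under a wrong lead-in. Protocol 12.5.2 plans laboratory listings, flags against normal ranges, summaries and shift tables, and marking by laboratory limits delivers that. No visible SAP output counts liver events from this table. Actual values are listed, ALT/AST rises above 5x ULN are recorded as AEs under Table 16-2, and scheduled post-baseline chemistry is sparse (first visit after a drug holiday, and follow-up). All of this stands and limits the size of the point. It does not remove it: the lead-in of 5.8.1 is wrong for the rows directly beneath it.

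The end of the table is not visible, so bilirubin and INR rows are not judged, and a later liver table cannot be ruled out. The SAP contents list shows only 5.8.1 under 5.8.

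Three stronger readings are tempting but not supported:

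- **An undeclared change to the protocol.** A reader might infer this because SAP section 4 mentions only the interim analysis ("Contrary to what was stated in the protocol, an interim analysis will be conducted"). But the protocol specifies no analysis of liver triggers or events, so there was no such change to declare.
- **The table hides the level at which treatment must stop.** SAP 5.8.1 claims to define triggers and events, not the action levels of Table 16-2. Nor is stopping a single laboratory level there: it also applies above 3x ULN with symptoms, and at more than 5x and up to 8x persisting beyond two weeks.
- **Particular values are misclassified in men or women.** The ALT/AST ULN is not given, and the classification turns on it. An AST of 200 U/l in a man is 200/50 = 4.0x (trigger) with a ULN of 50, but 200/37 = 5.4x (event) with a ULN of 37.

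**Conclusion.** The point holds, as a reporting defect of limited reach that should be corrected. The visible ALT and AST limits cannot be the Table 16-1 trigger and event limits under any ULN; this rests only on reading '+++' as about 800 U/l. That a trigger and an event can share '++' holds for any ULN from 20 to 160 U/l, given that a value is marked by the highest limit it exceeds. The ALP gap (above 208 and up to 300 U/l in women; above about 258 and up to 300 in men) rests on '+' being the ULN and, for men, on the µmol/sl row.

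The effect is on the flags in the laboratory safety listings. A reader might infer that liver monitoring or the safety conclusions are compromised. They are not: sites manage patients by the protocol's Appendix 2, AE reporting is separate, and neither the primary nor the secondary endpoints use these flags.

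**What to change.** In SAP 5.8.1:

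1. Derive liver trigger and liver event flags from the Table 16-1 multiples of each sample's own ULN.
2. Add the laboratory-based combined criteria where the component tests exist: ALT/AST >3x with INR >1.5; and ALT/AST >3x with total bilirubin >2x and no ALP >2x. INR appears in Protocol Table 8-3 under coagulation, but the visible row of the visit schedule names only chemistry and haematology, so its availability needs checking.
3. Retitle the present table, and reword its lead-in, as central-laboratory alert limits used for general abnormality flagging, in line with SAP 2.8.3.

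The cost is a small set of derived flags, a reworded sentence, and the ULN for each sample in the laboratory dataset. No new visits, samples or data collection are needed. If the sponsor wants only general laboratory alerts in this listing, step 3 with a reference to Protocol Table 16-1 is the minimum correction.
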